7 STUDY PROCEDURES

An overview of the study visits and evaluations schedule is presented in **Table 1: Schedule of Study Visits and Procedures.**

Scheduled visits for participants include the following;

- Screening
- Enrollment
- Follow up Visits (initial product use period: Weeks 4-12; visits at wk 4,8,12)
- Follow-up Visits (optional product use period: Weeks 13- 48; visits at wk 24,36,48)
- Final Study Visit (week 52)

7.1 SCREENING VISIT

Screening procedures may take place up to 40 days prior to a participant's enrollment. It is expected that, in most cases, all required screening procedures would be completed at one visit. However multiple visits may be conducted within this time period to complete all required screening procedures, if necessary. Written informed consent for screening is obtained before any screening procedures are initiated. For participants who do not meet the eligibility criteria, screening is discontinued once ineligibility is determined. If HIV-infection is identified as the reason for ineligibility, counseling and referral to appropriate treatment site will be performed.

Screening procedures are as follows:

- Administrative/Behavioural Procedures
 - Obtain written informed consent for enrollment, from participant and his/her parent or guardian
 - Assessment of understanding for informed consent form
 - Identification number assignment
 - Locator information
 - HIV pre-and post-test counseling, including risk reduction counselling
 - Provision of condoms
 - Schedule next visit (if applicable)

- Reimbursement.
- Clinical Procedures
 - Medical eligibility information
 - Medical history
 - Physical exam, including Tanner staging
 - Syndromic treatment for STI, if clinically indicated
 - Offer of STI testing and treatment for participant and partner(s) if indicated
 - Ascertainment of current contraceptive method and contraceptive counseling
 - Contraceptive counselling and provision of contraception as appropriate
 - Blood collection
 - Hep B vaccination if non-immune by serologic testing. (This will be given at 0,1 and 6 months; Wks 0,4, 24)
- Laboratory Procedures
 - HIV serology
 - Hepatitis B surface antibody and antigen testing (test results will be given to participants approximately one week after the test and vaccination will be provided during screening window)
 - Herpes (HSV-2), and a swab
 - Gonorrhea and Chlamydia *
 - Urine dip stick
 - Aspartate aminotransferase/alanine aminotransferase (AST/ALT) testing
 - Serum chemistries, including creatinine, glucose, electrolytes, and lipase
 - Full Blood Count
 - Urine pregnancy testing (for females)

* The swab will be self collected vaginal swab for girls and a urine test for boys.

7.2 ENROLLMENT VISIT

Day 0 for the participant will be the day of the Enrollment Visit:

- Administrative/Behavioural Procedures

- Locator information (update)
- Review of study procedures (ongoing consent)
- HIV pre-and post-test counseling, including risk reduction counselling
- Provision of condoms
- Eligibility assessment (including review of all screening documentation)
- Baseline sexual risk behavior questionnaire (for all enrolled participants)
- Reimbursement
- Schedule next visit (if applicable)

- Clinical Procedures
 - Review of all prior screening documentation
 - Update medical history and/or current medications, if applicable
 - Re-confirmation (by participant self-report) of medical eligibility information
 - Syndromic treatment for STI, if clinically indicated
 - Offer of STI testing and treatment for participant and partner(s) if indicated
 - Confirmation of current contraceptive method and contraceptive counseling
 - Contraceptive counselling and provision of contraception as appropriate
 - Disclosure of available test results, which must be made available to participant prior to administration of study product
 - Hepatitis B vaccination, if indicated
 - Update Medical History
 - Provision of study drug and instructions

- Laboratory Procedures
 - Urine pregnancy testing (for females)
 - HIV rapid testing
 - At all visits
 - As clinically indicated

7.3 FOLLOW UP VISITS (FOR WEEKS 4, 8, 12)

All enrolled study participants will complete 4 weekly follow-up visits for the first 12 weeks, targeted to occur every 28 days after the participant's study enrollment date (Day 0). Target dates are set based on the enrollment date, and do not change if subsequent actual visits take place before or after the target date. As it will not always be possible to complete monthly follow-up visits on the targeted dates, follow-up visits may be completed within an approximate 2-week window around the target date (-/+7 days from the target date). Thereafter visits will be 12 weekly with similar windows applying.

The following procedures will be completed at each initial Follow-Up Visits; Wks 4, 8, 12:

- Administrative/Behavioural Procedures
 - Locator information (update)
 - At all visits
 - HIV pre-and post-test counseling, including risk reduction counselling
 - At all visits
 - Social harms and/or benefits
 - At all visits
 - Sexual risk behavior questionnaire
 - At all visits
 - Acceptability questionnaire
 - At all visits
 - Provision of condoms
 - At all visits
 - Reimbursement
 - At all visits
 - Schedule next visit
 - At all scheduled visits, except Final Study Visit
- Clinical Procedures
 - Contraceptive counselling and provision as appropriate
 - At all visits
 - Targeted Physical exam

- As clinically indicated
- Update medical and menstrual history and/or current medications if applicable
 - At all visits
- Record/update adverse events (AEs) applicable
 - At all visits
- Hepatitis B vaccination, if indicated
 - At Enrollment (wk 0), month1 (Wk 4) and Month 6 (Wk 24)
- Provision of study drug and instructions
 - At weeks 4, 8 .
- Laboratory Procedures
 - HIV rapid testing
 - At all visits
 - As clinically indicated
 - STI testing
 - Herpes (HSV-2),
 - Chlamydia and Gonorrhea testing (wk 12 only)
 - Urine dip stick testing
 - Every 3 months; At wk 12 only
 - Aspartate aminotransferase/alanine aminotransferase (AST/ALT) testing
 - Every 3 months; at wk 12 only
 - Serum chemistries, including creatinine, glucose, electrolytes, and lipase
 - Every 3 months, at wk 12 only
 - Full blood count testing
 - Every 3 months; at wk 12 only
 - Haematocrit testing
 - Weeks 4 and 8
 - Urine pregnancy testing (for females)
 - At all visits
 - Contraceptive counseling
 - At all visits

- TDF/FTC drug levels via venous blood sampling and preparation of dried blood spots for storage.
 - At all visits, Wks 4, 8 and 12.

7.4 FOLLOW UP VISITS (AFTER WEEK 13 AND UP TO WEEK 48; VISITS AT 24, 36, 48)

For the initial product usage lead-in period (Weeks 4-12), study participants will be asked to adhere to the study product. After the 12 week lead in period, participants will be asked at subsequent 12 weekly visits whether they wish to continue PrEP, stop PrEP or restart PrEP as part of their prevention package (Week 12, 24 and 36). All participants regardless of product usage will be followed for the duration of the study. Participants will be advised to make these decisions at scheduled study visits. Reasons for decision will be enquired upon and recorded in CRFs.

Participants will also however be told they can contact study site at any time and also when they should with-hold PrEP for medical reasons.

Participants will complete scheduled 4 weekly follow-up visits until week 12. Thereafter, all visits will be 12 weekly regardless of PrEP addition to the prevention package or not. Target dates are set based on the enrollment date, and do not change if subsequent actual visits take place before or after the target date.

As it will not always be possible to complete follow-up visits on the targeted dates, follow-up visits may be completed within an approximate 2-week window around the target date (-/+7days from the target date).

The following procedures will be completed at each Follow-Up Visit (wks 24, 36, 48):

- Administrative/Behavioural Procedures
 - Locator information (update)
 - At all visits
 - HIV pre-and post-test counseling, including risk reduction counselling
 - At all visits
 - Social harms and/or benefits
 - At all visits
 - Sexual risk behavior questionnaire

- At all visits
- Provision of condoms
 - At all visits
- Provision of study drug (for participants who choose to receive study product)
 - at visits Wk 12, 24, 36 .
- Acceptability assessment
 - at visits Wk 12, 24, 36, 48.
- Adherence Counselling (if participant is on study product)
 - at visits Wk 12, 24, 36, 48 (week 48 visit will be feedback on last 3 months only since no more product will be offered).
- Feedback of plasma drug level/DBS results (to participants on study product who agree to receive this information at the time of adherence counseling.)
 - At visits Wk 12, 24, 36, 48.
- Adherence assessment (including pill counts) and counselling (for participants who choose to receive study product)
 - At visits Wk 12, 24, 36, 48
- Study drug supplies and instructions/counseling (for participants who choose to receive study product)
 - At all visits where study product is administered week 12, 24, 36
- Reimbursement
 - At all visits
- Schedule next visit
 - At all scheduled visits, except Final Study Visit
- Clinical Procedures
 - Contraceptive counselling and provision as appropriate
 - At all visits
 - Physical exam
 - At week 48
 - As clinically indicated
 - Update medical and menstrual history and/or current medications if applicable

- At all visits
- Record/update adverse events (AEs) applicable
 - At all visits
- Laboratory Procedures
 - HIV rapid testing
 - At all visits
 - As clinically indicated at unscheduled visits (reported exposures)
 - STI testing
 - Herpes (HSV-2),
 - Chlamydia, and Gonorrhea testing (0, 12, and 48 weeks)
 - Urine dip stick testing
 - Every 12, 24, 36, 48 weeks
 - Aspartate aminotransferase/alanine aminotransferase (AST/ALT) testing
 - Every 12, 24, 36, 48 weeks
 - Serum chemistries, including creatinine, glucose, electrolytes, and lipase
 - Every 12, 24, 36, 48 weeks
 - Full Blood Count testing
 - Every 12, 24, 36, 48 weeks
 - Urine pregnancy testing (for females)
 - At all visits
 - Contraceptive counseling
 - At all visits
 - Measurement of study drug levels by Plasma/DBS
 - At 12, 24, 36, 48 weeks.

7.5 INTERIM VISITS

Participants may make interim contacts and unscheduled visits at their request, or as deemed necessary by the Site Investigator or designee, at any time during the study. All interim contacts and unscheduled visits will be documented in the participant's study file. When an interim contact or unscheduled visit occurs in response to AEs, a study clinician will clinically assess the reported

event and provide, or refer the participant for, appropriate medical care. Study participants will be instructed to contact their study clinic in the event of any AE. Participants will also be instructed to seek immediate emergency care (even from other providers) if they consider they require it. The AE will be reported on the appropriate CRF.

Some examples of reasons for an interim visit are:

- To report an AE;
- To get more condoms or study product;
- To address any contraceptive needs;
- To ask questions of study staff;
- To discuss problems with study adherence;
- To perform an interim examination (e.g., follow-up on an AE or participant request); and
- To provide lab results not available at the last follow-up visit.

If a participant is contacted when s/he missed a visit, staff will try to obtain her reasons for missing a visit. This information may be used to try to improve overall retention in the study.

7.6 FINAL STUDY VISIT (WEEK 52) OR TERMINATION VISIT (AND AT THE TIME OF ANY PERMANENT STUDY PRODUCT TERMINATION OR STUDY PRODUCT DISCONTINUATION)

Participants who reach week 52 will follow procedures included in the table of study procedures on page 72. This includes provision of any outstanding test results and final interviews. In addition a DBS/ plasma will be performed for drug levels at the final study visit.

Participants who have chosen to discontinue the product prior to the routine protocol-required withdrawal at Week 52 should continue routine follow-up visits. All protocol-required interviews and procedures, besides study product administration and drug levels, should be continued until Final Study Visit.

If a participant discontinues study product following instruction from the Investigator or wishes to withdraw permanently from the study, visit procedures as per week 48 will be conducted. The participant will then return for a final study visit (week 52) if possible.

The following procedures will be completed the final visit (wk 52 the final visit):

- Administrative/Behavioural Procedures
 - Locator information (update)
 - At all visits
 - HIV pre-and post-test counseling, including risk reduction counselling
 - At all visits
 - Social harms and/or benefits
 - At all visits
 - Sexual risk behavior questionnaire
 - At all visits
 - Provision of condoms
 - At all visits.
 - Acceptability assessment
 - Wk 52.
 - Feedback of plasma drug level/DBS results (to participants on study product who agree to receive this information at the time of adherence counseling.)
 - At visits Wk 12, 24, 36, 48.
 - Reimbursement
 - At all visits
- Clinical Procedures
 - Contraceptive counselling and provision as appropriate
 - At all visits
 - Physical exam
 - As clinically indicated
 - Update medical and menstrual history and/or current medications if applicable
 - At all visits
 - Record/update adverse events (AEs) applicable
 - At all visits
- Laboratory Procedures
 - HIV rapid testing

- At all visits
- Aspartate aminotransferase/alanine aminotransferase (AST/ALT) testing
 - Wk 52
- Serum chemistries, including creatinine, glucose, electrolytes, and lipase
 - Wk 52
- Urine pregnancy testing (for females)
 - At all visits
- Contraceptive counseling
 - At all visits
- Measurement of study drug levels by DBS for those participants on study prout up to and including wk36
 - Wk 52

7.7 CLINICAL EVALUATIONS AND PROCEDURES

Full physical exams will be performed at screening and week 48 and targeted exams will be performed at other study visits as required. Clinical symptoms will be systematically assessed in a structured medical history at screening and enrollment (wk 0), Wks 4, 8, 12 and then every 12 weeks for the length of the trial.

Full physical exams include the following assessments:

Vital signs:

- Oral temperature
- Blood pressure
- Pulse
- Respirations

Measurements of:

- Weight
- Height

Clinical assessments of:

- Head and eyes
- Ears, nose, and throat
- Neck
- Lymph nodes
- Heart
- Lungs
- Abdomen
- Extremities
- Neurological
- Skin
- Breasts
- Tanner stage

Additional assessments may be performed at the discretion of the examining clinician in response to symptoms or illnesses present at the time of the exam.

7.8 LABORATORY EVALUATIONS AND PROCEDURES

Laboratory evaluations will include the following:

- Hepatitis B surface antigen and antibody testing
 - At Screening
- Urine pregnancy test
 - At every visit
- HIV serology
 - At every visit
- HSV-2 serology
 - At screening, Week 12, 48
- Chlamydia, and Gonorrhea.

- At screening, Week 12, 48
- Serum chemistries, creatinine only
 - Week 52
- AST, ALT
 - Screening, Week 12, 24, 36, 48 and 52
- Full Blood Count
 - Screening, Week 12, 24, 36, 48
- Haematocrit
 - Week 4, 8, 52
- DBS / Plasma drug level sampling
 - Week 4, 8, 12, 24,
 - Week 36, 48, for those who remain on study product
 - Week 52, Plasma only for those who remain on study product
- Urine dip stick
 - Screening, Week 12, 24, 36, 48

The location of laboratory evaluations will depend on laboratory capacity.

7.9 BEHAVIOURAL EVALUATIONS AND PROCEDURES

Using interviewer administered questionnaires the following behaviors of participants will be recorded and assessed over the 52 weeks of study participation at scheduled study visits:

- Study product adherence, with measures of barriers and facilitators of adherence (for focus group with enrolled participants who receive study product), including a visual scale.
- Product acceptability
- Sexual activity

- Condom use, including frequency of condom use when having sex and condom use at last sex
- Willingness to have real time drug level data and reasons for or against.
- Estimation of drug levels if not willing to have data shared.

All focus groups will be conducted by a study staff member, who will be trained by an expert socio-behavioural researcher. Focus groups will address a number of questions including adolescents' attitudes towards PrEP; adolescent perceptions of taking drugs previously reserved for HIV treatment as a form of prevention; where they would like to access these drugs; whether taking PrEP might identify individuals as high-risk and therefore stigmatise them; whether enhanced protection against HIV infection provided by PrEP might lead to sexual disinhibition or risk compensation; whether adolescents will/do still use condoms in order to protect against other STI's; what factors (e.g. appearance changes as a result of drug side-effects) might/do impact on adherence; where adolescents would like to access the drugs. They will also examine willingness to have drug levels shared and impact of hearing actual drug levels during counseling.

Parental/ guardian consent and adolescent assent will be obtained for all focus group participants (see Appendices 16.3 and 16.4).

7.10 PROCEDURES FOR PARTICIPANTS WHO TEMPORARILY HOLD OR DISCONTINUE STUDY PRODUCT

7.10.1 Participants Who Become Infected with HIV

If a participant becomes HIV-infected at any time after enrolment into the study, the study product will be immediately terminated (if applicable) and the protocol-specified visit schedule will be followed, for participants who choose to be maintained in the study. In addition, extra interim visits will be added to their schedule for psychosocial support, if needed. These visits will occur in addition to study visits, although they can be combined with regularly-scheduled study visits.

If a participant tests positive on two rapid HIV antibody rapid tests, they will be considered HIV-infected and will receive post-test counseling on these results. Participants with an indeterminate

HIV test result will be asked to provide a blood sample for ELISA testing, to confirm whether they are HIV-infected.

Participants will be allowed as much time and given as much support as they need to cope with the positive result. The counselor disclosing the result will encourage the participant to identify a trusted adult (not necessarily the parent/ guardian) that they would like to disclose to. If necessary, this adult will be called into the clinic to help support the participant [see Section 16.5 for more detail, including the HIV testing algorithm].

The participant will also be given a referral letter for counseling and support in the community. The participant will also be reassured that they can return to the clinic at any time during clinic hours for support. Clinic staff will make telephone contact with the service to which they are referring the participant.

If both rapids are positive blood will be sent for confirmatory viral load testing. When these results are available the participant will be recalled and following another pretest information session, a blood sample for CD4 count as well as resistance and genotype testing will be obtained. The participant will be followed up at the study site for the duration of the study, and will receive a CD4 count at 3-monthly intervals and psychosocial support for disclosure, to ensure that initial care and counselling is well-managed. After the Final Study Visit, the research team will link the participant into long-term HIV care and treatment at one of the existing local health facilities.

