9.6 MANAGEMENT OF HIV INFECTION

Refer to Section 7.10.1 for specific study procedures regarding participants who become infected with HIV at any time during the study.

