 - If this occurs at screening, the counseling staff/study physician explains to the participant that inclusion in study is not possible and refers the participant to a service provider/ clinic for further evaluation, management and support.
 - If a participant tests positive at any other visit, they can remain in the study and complete all study activities as planned including continuing to receive the vaccine (if they have consented to receive it). Further visits for psychosocial support and clinical management should be planned with the participant, per site-specific procedures.
 - Personalized referral to services for long term clinical management, and follow-up to ensure adolescent attendance should take place
 - Details of any community support groups and other relevant organizations should be passed on to the participant

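### Section 7.10.1 places linkage to long-term HIV care after week 52, while Appendix 16.5(d) lists referral once infection is confirmed, and the protocol does not reconcile the two

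*Protocol*

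**What the plan says.** Section 9.6 of the protocol, on management of HIV infection, consists of one pointer: "Refer to Section 7.10.1 for specific study procedures regarding participants who become infected with HIV at any time during the study".

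Section 7.10.1 stops study product at once and keeps the participant in follow-up at the study site. After two positive rapid tests it orders a viral load, then CD4, resistance and genotype tests. It provides a referral letter for counselling and community support, a telephone call to that service, and CD4 counts every 3 months. Site follow-up also includes "psychosocial support for disclosure, to ensure that initial care and counselling is well-managed". The section ends: "After the Final Study Visit, the research team will link the participant into long-term HIV care and treatment". Section 7 sets the Final Study Visit at week 52.

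Appendix 16.5(d) lists what happens when a positive result is confirmed. Staff discuss treatment options with the participant. For a participant already in the study, "Further visits for psychosocial support and clinical management should be planned with the participant, per site-specific procedures". The list then adds: "Personalized referral to services for long term clinical management, and follow-up to ensure adolescent attendance should take place".

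Section 14 (Standard of care) says that any seroconversion is referred to the local health facility, with help in reaching treatment. It states no time, and it directs the reader to a Section 7.8.1 for the full procedures.

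**The concern.** Staff who look up how to manage a new infection are sent by Section 9.6 to Section 7.10.1. The only sentence there about HIV treatment places linkage after the last visit. The early referral letter in that section is for counselling and community support, not treatment. A site that followed 7.10.1 to the letter would therefore link an adolescent to HIV treatment later than the protocol's own appendix calls for.

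Two comparisons within the protocol make this look unintended. Under Section 7.1, a person found HIV-positive at screening is referred to a treatment site. Under Section 7.10.3, a participant with hepatitis B confirmed during the study is referred for care. Neither passage defers the step to study end.

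What is at stake is the care of participants as young as 15 and the clarity of one instruction. The SAP dates seroconversion from the last negative and first positive tests, so the HIV incidence analysis does not depend on when linkage occurs.

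**Working it through.** There is no power or precision figure to reproduce. The check is a comparison of passages, followed by one subtraction.

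**Passages side by side**

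| Place | Step described | When |
|---|---|---|
| 7.10.1, last sentence | Linkage to long-term HIV care and treatment | After the Final Study Visit (stated) |
| Appendix 16.5(d) | Personalised referral for long-term clinical management, with attendance follow-up | Once a positive result is confirmed (implied by the item's heading; no deadline) |
| Section 14, Standard of care | Referral of any seroconversion to the local health facility | No time given |
| 9.6 | Pointer to 7.10.1 | Adds none |

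So one time is stated, one is implied by a heading, and one is absent. A passage without a time cannot contradict 7.10.1. Section 14 is consistent with the earlier referral and is not a third timing.

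**Size of the gap if 7.10.1 is followed without 16.5**

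Inputs: the Final Study Visit is at week 52 and follow-up visits are at weeks 4, 8, 12, 24, 36 and 48 (Section 7). HIV is tested at every visit (Section 7.8).

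Gap = 52 - week of detection:

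- week 4: 52 - 4 = 48 weeks
- week 8: 52 - 8 = 44 weeks
- week 12: 52 - 12 = 40 weeks
- week 24: 52 - 24 = 28 weeks
- week 36: 52 - 36 = 16 weeks
- week 48: 52 - 48 = 4 weeks
- week 52: 52 - 52 = 0 weeks

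Because linkage comes after the visit, these are minimum gaps on that reading, for participants who stay to week 52 and are detected at a scheduled visit. Under 16.5(d) no such gap arises.

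**Early leavers.** Section 14 and 16.5(d) apply to them as written. Only the 7.10.1 sentence depends on the Final Study Visit.

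**Cross-references.** Section 7.8 covers laboratory evaluations and has no subsection 7.8.1; the procedures Section 14 means are in 7.10.1. Appendix 16.5 says that a participant who tests positive can "complete all study activities as planned including continuing to receive the vaccine (if they have consented to receive it". It does not say that study product stops, and it does not name the vaccine. The study does give hepatitis B vaccine to non-immune participants, with the last dose at about week 24 (Sections 7.1, 7.3, 7.10.3 and 9.2).

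**The case against.** The strongest reply is that the passages describe two steps. Section 14 and 16.5 speak of referral. Section 7.10.1 speaks of linkage into long-term care straight after describing site-managed follow-up, so its last sentence can be read as the hand-over when the site's role ends. Section 7.10.1 also refers staff to the appendix ("see Section 16.5 for more detail, including the HIV testing algorithm"), so the 48-week case requires ignoring a pointer in the same section. HIV treatment during participation is contemplated elsewhere: Section 13.4 lists it among the procedures to which adolescents consent themselves, and Section 13.3 promises management of identified conditions through referral.

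Much of this stands. The hand-over reading is plausible, and the text is better called unreconciled than contradictory. But the protocol nowhere says that referral comes first and hand-over later, and the visible text does not define the initial care that the site manages. The pointer to 16.5 follows the text on disclosure to a trusted adult and mentions the testing algorithm, not linkage.

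A reader might go further in three ways that the documents do not support:

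- **That treatment will be deferred by up to 48 weeks.** Appendix 16.5(d) and Section 14 both call for referral, and nothing in 7.10.1 forbids earlier treatment.
- **That infected participants could continue FTC/TDF under the 16.5 wording.** Section 7.10.1 stops product immediately, and Section 6.3.1 limits dispensing to participants with negative HIV tests.
- **That the vaccine wording is simply left over from another study.** It may be, but a participant who seroconverts before about week 24 could still be due a hepatitis B dose, so the line should not just be deleted.

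**Conclusion.** The point holds as an unreconciled instruction on participant care, and it should be fixed. Section 7.10.1, to which 9.6 defers, places linkage to long-term HIV care and treatment after week 52 and names no earlier route to treatment. Appendix 16.5(d) lists referral once infection is confirmed.

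The gap runs from 48 weeks (detection at week 4) to 0 (detection at week 52), and only if 7.10.1 is followed without 16.5. It is not an expected delay, and no number of affected participants is claimed. No endpoint, analysis or sample size changes.

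This rests on the visible protocol text. The consent pages, the full follow-up testing algorithm (16.7) and the site procedures to which 16.5 defers could not be checked, and they may already settle the timing. Confidence is high that the wording does not line up; there is no evidence that care would in fact be late.

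**What to change.** 1. Replace the last sentence of Section 7.10.1 with:

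> When HIV infection is confirmed, the research team will refer and link the participant to HIV care and treatment at a local health facility and follow up attendance (see Appendix 16.5), including participants who leave the study early; study-site follow-up continues in parallel, with a final hand-over at the Final Study Visit.

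2. In Appendix 16.5, replace the wording on completing all activities and continuing the vaccine. State that participants who test positive may remain in the study and follow the visit schedule, that FTC/TDF is stopped immediately (see 7.10.1), and that any hepatitis B vaccine series still due may be completed.

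3. In Section 14, change the pointer from 7.8.1 to 7.10.1. This is clerical.

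The changes add no visits, tests or participants, and attendance follow-up is already in 16.5. If made as a full version amendment, they need the ethics, regulatory and registration steps in Sections 13.1 and 13.2.
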